2.6 Recruitment

Subjects are recruited at local pharmacies, sport clubs and notice boards of local coliseums using information flyer. The subjects will be recruited from the investigational sites subject pool and public advertisement. Potential participants of the study are asked by the investigator to join the investigation.

A subject will only be admitted to the study if all inclusion and none of the exclusion criteria are met. Potential subjects will be screened for study eligibility. A subject is considered enrolled after:

- Written Informed Consent is obtained
- Meeting Inclusion and Exclusion criteria

2.7 Consent

An investigator will explain to the subjects the nature, significance and implications of the study prior to any Clinical Investigation related examination. The investigator will explain all methods, rules of conduct and any restrictions which may apply. Possible effects and side effects will be discussed. Subjects will be informed that they are free to withdraw from the study at any time, without giving any reason for doing so. They must be able to understand the full implications of their decision.

All participants will sign an informed consent form as evidence of consent.

The subject information sheet and the informed consent form of each participant will be filed in the Investigator Site File. A second original (or copy) of the signed consent form and a copy of the information sheet will be handed to the subjects after signature and before enrollment.

2.8 Procedure

	Examination schedule	responsible	time in minutes								
preparation											
1.	pre-treatment discussion	investigator									
2.	read Informed Consent Form	subject									
3.	check inclusion and exclusion criteria	investigator									
4.	sign Informed Consent Form incl. Consent for processing personal data	subject									
5.	if all criteria are fulfilled undress subject	subject									
source data											
6.	enter patient name and ID in source data doc.	investigator									
7.	enter date of examination, date of birth and gender in source data doc.	investigator									
8.	check if signed Informed Consent Form is available	investigator									
10.	check inclusion and exclusion criteria	investigator									
create subject file in PC software seca analytics 115											
11.	start seca analytics 115	investigator									
12.	login as user named "BCA-12"	investigator									
13.	create new subject file	investigator									
14.	enter subject ID, gender, date of birth and select the ethnicity	investigator									
15.	save subject data	investigator									
mBCA 515 measurement in standing position											
16.	start mBCA 515	investigator									
17.	go to patient tab	investigator									
18.	enter subject ID and click on search	investigator									
19.	select subject to be measured	investigator									
20.	go to weight & height tab	investigator									
21.	ask subject to take shoes off	investigator									
22.	measure subject height with seca 274 and send it wirelessly to the mBCA 515	investigator									
23.	ask subject to take socks off	investigator									
24.	step on mBCA 515 glassplattform	subject									
25.	weight is measured and BMI is calculated automatically	mBCA									
26.	click on BIA tab	investigator									
27.	State whether the subject meets the mBCA contraindications or not	investigator									
28.	Yes: the measurement is not performed.	investigator									
29.	No: the procedure continues. The dialog window for positioning the patient appears.	investigator									
30.	Ensure that the patient is standing on the device correctly:	investigator									

  
 Test point	Characteristics	
   
 Hands	 
 Hands must be clean Same pair of hand electrodes on left and right Select the pair of hand electrodes such that arms are extended but not under strain Finger spacers of the hand electrodes between the middle finger and ring finger on both sides 	
 
 Feet	 
 Stand on device with bare feet Feet must be clean Heels on the rear foot electrodes Balls of feet on the front foot electrodes 	
 
 Position	 
 Upright position Knees slightly bent Do not move during the measurement 	
  
				Test point	Characteristics	Hands	
 Hands must be clean Same pair of hand electrodes on left and right Select the pair of hand electrodes such that arms are extended but not under strain Finger spacers of the hand electrodes between the middle finger and ring finger on both sides 	Feet	
 Stand on device with bare feet Feet must be clean Heels on the rear foot electrodes Balls of feet on the front foot electrodes 	Position	
 Upright position Knees slightly bent Do not move during the measurement
Test point	Characteristics										
Hands	
 Hands must be clean Same pair of hand electrodes on left and right Select the pair of hand electrodes such that arms are extended but not under strain Finger spacers of the hand electrodes between the middle finger and ring finger on both sides 										
Feet	
 Stand on device with bare feet Feet must be clean Heels on the rear foot electrodes Balls of feet on the front foot electrodes 										
Position	
 Upright position Knees slightly bent Do not move during the measurement 										

Examination schedule	responsible	time in minutes								
31. If the patient is in correct contact with an electrode pair, the corresponding electrode indicator on the touchscreen display will be green. As soon as all the electrode indicators on the touchscreen display are green, a countdown to the start of measurement appears. Measurement starts automatically.	mBCA									
32. Remaining measurement time is displayed.	mBCA									
33. As soon as the measurement ends, the message End of measurement appears.	mBCA									
34. Press the continue button	investigator									
35. enter PAL value and waist circumference	investigator									
36. Press the save button	investigator									
37. check in seca analytics 115 if measurement data was saved	investigator									
38. inform subject to put socks and shoes back on	investigator									
measurement with mBCA 555		3								
37. start PC software for mBCA 555	investigator									
38. enter subject ID	investigator									
39. select handrail position	investigator									
40. step on mBCA 555 glassplattform	subject									
41. Ensure that the patient is standing on the device correctly:	investigator									

  
 Test point	Characteristics	
   
 Hands	 
 Hands must be clean Same pair of hand electrodes on left and right Select the pair of hand electrodes such that arms are extended but not under strain Finger spacers of the hand electrodes between the middle finger and ring finger on both sides 	
 
 Feet	 
 Stand on device with bare feet Feet must be clean Heels on the rear foot electrodes Balls of feet on the front foot electrodes 	
 
 Position	 
 Upright position Knees slightly bent Do not move during the measurement 	
  
			Test point	Characteristics	Hands	
 Hands must be clean Same pair of hand electrodes on left and right Select the pair of hand electrodes such that arms are extended but not under strain Finger spacers of the hand electrodes between the middle finger and ring finger on both sides 	Feet	
 Stand on device with bare feet Feet must be clean Heels on the rear foot electrodes Balls of feet on the front foot electrodes 	Position	
 Upright position Knees slightly bent Do not move during the measurement
Test point	Characteristics									
Hands	
 Hands must be clean Same pair of hand electrodes on left and right Select the pair of hand electrodes such that arms are extended but not under strain Finger spacers of the hand electrodes between the middle finger and ring finger on both sides 									
Feet	
 Stand on device with bare feet Feet must be clean Heels on the rear foot electrodes Balls of feet on the front foot electrodes 									
Position	
 Upright position Knees slightly bent Do not move during the measurement 									
42. If the patient is in correct contact with an electrode pair, start the measurement with the PC software	investigator									
43. As soon as the measurement ends, the message "BIA measurement: OK" appears --> measurement must be saved manually	investigator									
mBCA 525 measurement in standing position		5								
44. keep subject standing	investigator									
45. start mBCA 525	investigator									
46. login as user "BCA-12"	investigator									
47. select subject file to be measured	investigator									
48. enter weight, height, PAL and waist circumference	investigator									
49. click on BIA tab	investigator									
50. follow instructions on the monitor screen	investigator									
51. save measurement data	investigator									
52. check in seca analytics 115 if measurement data was saved	investigator									
mBCA 525 measurement in lying position		15								
53. make sure subject lays down for 10 min.	investigator									
54. login as user "BCA-12"	investigator									
55. select subject file to be measured	investigator									
56. enter weight, height, PAL and waist circumference	investigator									
57. click on BIA tab	investigator									
58. follow instructions on the monitor screen	investigator									
59. save measurement data	investigator									
60. check in seca analytics 115 if measurement data was saved	investigator									

Examination schedule	responsible	time in minutes
blood drawing		25
61. take baseline blood sample (30ml)	investigator	
62. calculate NaBr and D2O amount based on body weight	investigator	
63. weigh D2O within a flask	investigator	
64. add NaBr to the fluid and solve the dry chemical within the fluid D2O	investigator	
65. ask subject to drink the solution quickly	investigator	
66. inform subject not to drink within the next 4 hours	investigator	
67. after 4h take the next blood sample (30ml)	investigator	
DXA measurement		30
68. accompany the subject to the clinic of radiology (UKSH, Kiel)	investigator	
69. starting QDR program on the DXA connected PC	investigator	
70. click on daily quality control tab	investigator	
71. measure the spine phantom for quality control	investigator	
72. wait for "systemcheck successful" note	investigator	
73. click ok tab	investigator	
74. get undressed to underwear and remove all metal items (piercings etc)	subject	
75. click measurement tab	investigator	
76. click new patient tab	investigator	
77. enter data (code, height, weight, date)	investigator	
78. select whole body scan	investigator	
79. position subject on measurement table	investigator	
80. click measurement tab	investigator	
81. after measurement is completed click analysis tab	investigator	
82. click results tab	investigator	
83. click finish tab	investigator	
84. click report tab	investigator	
85. print results	investigator	
ADP measurement		15
86. start BODPOD software	investigator	
87. get undressed to underwear and put on a bathing cap	subject	
88. enter data to the software (code, height, gender, birthday)	investigator	
89. measure weight using the connected scale	investigator	
90. measure the volume of a standardized cylinder	investigator	
91. inform the subject to enter the measurement chamber	investigator	
92. close BODPOD door	investigator	
93. measure subjects volume	investigator	
94. click results tab	investigator	
95. print results	investigator	
MRI measurement		30
96. accompany the subject to the Department of Internal Medicine III (UKSH, Kiel)	investigator	
97. subjects get undressed to underwear and remove all metal items (piercings etc)	investigator	
98. place subject on the MRI scanner table	investigator	
99. place hearing conservation on subjects ears	investigator	
100. conduct whole body MRI scan (15 Min)	investigator	
101. MRI software is programmed by a trained radiological assistant	radiological assistant	
after completed measurement assist subject by leaving the MRI measurement		
102. table	investigator	
103. get dressed again	subject	
104. save MRI data on a CD	investigator	
Handgrip strength*		10
105. adjust dynamometer to subject	investigator	
106. set dynamometer needle in 0-position	investigator	
check subject position: relaxed; elbow 90° bent; shoulder, lower arm and wrist		
107. in neutral position	investigator	
108. hold dynamometer relaxed in right or left hand	subject	
109. press with maximal power	subject	
110. write down measured value	investigator	
111. reset dynamometer needle in 0-position	investigator	
112. repeat procedure (102. to 105.) 2 times	investigator & subject	

*Handgrip strength is measured with a dynamometer manufactured by Saehan for quality assessment of muscle mass.

seca	Clinical Investigation Plan Inv. code: BCA-12 Doc. code: 25-02-02-456	Rev. date: 16-01-19 Revision: 1.4 Page: 25 of 32
-------------	---	--

3. STUDY STATISTICS

The biometric sample size calculation for the previous study BCA-01 (AZ 111/11) was carried out by the Coordination Centre for Clinical Studies (KKS) of the Charité, [name], [name], Germany under the direction of [name]. The study BCA-01 included subjects from 18 to 65 years.

For target variable measurement resistance of the left body side (RI 50 kHz) was chosen. This provides, according to preliminary tests done by the investigator, the best approach to gain the most relevant medical results for formula generation. The precision (confidence interval width for μ) of all other variables was varied in a way that maximum (superior sample size) will always be found in the resistance measurement of the left body side (RI 50 kHz) being crucial for formula generation. The resulting sample size to generate a formula was N = 124 in the study BCA-01.

This number of 124 subjects is the basis for the calculation of the sample size in the current study BCA-12 for formula generation in older people.

The smaller age range that shall be examined in comparison to study BCA-01 is opposed to a greater change in body composition with high age. So no adaptation of sample size for these reasons is planned.

To achieve an overlap in the age range with the previous study BCA-01 additional 26 subjects between 60 and 65 years shall be examined.

The resulting sample size to generate a formula for elderly is N = 150.

This number allows a homogenous age distribution from 60 - 80 years. Older subjects will be examined as far as they can be recruited.

The prediction equations shall be developed by stepwise multiple regression analysis.

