1.2 Study Rationale

The study is based on the clinical trial BCA-01 (AZ 111/11) "Generation of prediction equations to analyze body composition of obese adults based on Bioelectrical Impedance Analysis (BIA)" and implicates an extension of the study collective.

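### The stated basis for N = 150, a confidence interval for a mean with resistance as target variable, says nothing about how accurately the equations predict body composition in the elderly

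*Combined protocol and SAP*

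**What the plan says.** Section 3, repeated in the synopsis under study statistics, builds the sample size in four steps.

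- **Target variable (BCA-01).** "For target variable measurement resistance of the left body side (RI 50 kHz) was chosen".
- **Criterion.** "The precision (confidence interval width for μ) of all other variables was varied", in such a way that the largest sample size "will always be found in the resistance measurement of the left body side (RI 50 kHz) being crucial for formula generation". No SD, interval width or confidence level is given. The outcome is stated as: "The resulting sample size to generate a formula was N = 124 in the study BCA-01".
- **Carry-over.** "This number of 124 subjects is the basis for the calculation of the sample size in the current study BCA-12". BCA-01 covered ages 18 to 65, and section 1.2 gives its title as "Generation of prediction equations to analyze body composition of obese adults". BCA-12 enrols people over 60 with no BMI criterion (section 1.8). Section 3 argues that the narrower age range and the larger changes in body composition at high age work against each other, and concludes: "So no adaptation of sample size for these reasons is planned".
- **Add-on.** A further 26 subjects aged 60-65 are included to overlap with BCA-01. Then: "The resulting sample size to generate a formula for elderly is N = 150". The plan adds that this number permits an even spread of ages from 60 to 80.

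The planned analysis is one sentence naming stepwise multiple regression. Section 1.4 lists the quantities to be predicted (FFM, TBW, ECW, VAT, total and segmental SMM). It places the reference methods on one side of the regression and impedance on the other.

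**The concern.** A sample size offered as what is needed to produce an equation should rest on something about the equation: expected R², residual SD, limits of agreement, or the number of candidate terms. Here the named criterion concerns the mean of a variable, and the variable that decides N is a predictor. Mean resistance could be estimated very precisely while the equation for VAT or ECW predicts poorly, or the reverse.

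Two things are at stake. First, the reader cannot tell what accuracy 150 subjects can establish for any compartment, device or position. Second, the plan mentions no internal validation. If the reported error comes from the same 150 subjects used to select and fit the terms, it will be too small, and nothing in section 3 says by how much. Section 9.2 says the results are intended for publication.

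**Working it through.** **1. The plan's own figure.** 124 + 26 = 150 reproduces exactly. The 124 cannot be reproduced, because SD, interval width and confidence level are not given. It is unverifiable here, not shown to be wrong.

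**2. What a precision-of-mean criterion delivers.** The half-width of a 95% CI for a mean, in units of that variable's SD, is t(0.975, n-1)/√n.
- n = 124: 1.979/√124 = 0.178 SD
- n = 150: 1.976/√150 = 0.161 SD

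The formula has no residual SD, no R² and no number of predictors. The result is the same whether the equation predicts well or badly.

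**3. What 150 delivers for an equation.** Assumptions: 150 complete subjects, p = 5 retained predictors (not in the documents), and terms treated as fixed in advance.
- Residual df = 150 - 5 - 1 = 144. The 95% CI for the residual SD, as a multiple of the estimate, runs from √(144/179.11) = 0.897 to √(144/112.67) = 1.131, or about -10%/+13%. For p from 3 to 10 it stays close to 0.90 to 1.13.
- The 95% CI half-width for each limit of agreement is 1.96 × √(1/n + 1.96²/(2(n-1))) = 1.96 × √(0.00667 + 0.01289) = 0.274 SD of the differences.

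**4. Is 150 enough?** That depends on a target the plan does not state. Two illustrative targets for the upper 95% limit of the residual SD:
- at most 1.15 times the estimate: 113 residual df, so n of about 117 to 124 for p = 3 to 10; 150 is enough
- at most 1.10 times the estimate: 233 residual df, so n of about 237 to 244; 150 is not enough

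**5. Optimism from stepwise selection.** The documents fix neither the candidate list nor an entry rule. The devices supply many values: the mBCA 515 records 19 frequencies × 7 segments × 4 quantities = 532, and the 525 and 555 record 9 × 7 × 4 = 252 each. These are strongly related, so the effective number is far smaller. As an illustration, forward selection was simulated with n = 150, entry at 0.05, 5 strong true predictors, and candidates either independent or correlated at 0.7 (600 runs per setting). The understatement of new-subject error was:

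| Candidates | Uncorrected error, √(RSS/n) | Standard error of the estimate, df-adjusted |
|---|---|---|
| 20 | about 6-7% | about 4-5% |
| 40 | about 11% | about 8% |

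The df adjustment for retained terms removes only part of the bias, because it does not count the terms that were tried and dropped. Weaker true predictors or a looser entry rule would change these values.

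**The case against.** The strongest reply is that section 3 makes no numerical accuracy claim. It says only that this many subjects are needed to build an equation, and a residual SD known to within -10%/+13% is respectable for that purpose. This stands. A reader might infer that 150 is too small. The documents do not support that, since step 4 shows the answer turning on an unstated target.

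Other readings also go further than the text allows:
- A reader might take all 150 as derived in BCA-01. Only 124 was. The other 26 have their own stated purpose, age overlap, and the plan separately links 150 to an even age distribution.
- A reader might take it as stated that resistance itself was sized by a CI for its mean. The text attaches that criterion to the other variables. That it also governed resistance is a strong inference, because the resulting sample sizes were compared on the same footing, but it remains an inference.
- A reader might say that the SD was borrowed from obese adults. No SD appears in the documents, and the obese population rests on the BCA-01 title alone.

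It can also be objected that validation is a separate issue from sample size. In part it is. But once the stated basis for N is seen not to bear on accuracy, the error estimate from these 150 subjects is the only accuracy evidence the study will have, so how it is computed belongs to the same correction.

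**Conclusion.** The point holds in limited form. The stated basis for 124, and so for 150, does not bear on the accuracy of the equations, and its transfer to people over 60 rests on an offset argument in which neither effect is quantified. The documents do not show that 150 is inadequate.

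The practical consequence is moderate. Before selection is allowed for, 150 complete subjects give the precision in step 3. Stepwise selection without correction would then make the reported error too favourable, by roughly 4-11% depending on the error measure and on whether 20 or 40 candidates are tried.

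These sizes rest on assumed numbers of predictors, an assumed entry rule, strong true predictors, and complete data for every equation. The last may not hold: section 1.9 says that discontinued subjects are not replaced, and N contains no allowance for losses. The conclusion about the basis for N needs none of these assumptions.

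**What to change.** Keep N = 150. In section 3 and the synopsis:

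1. Say that 124 was a precision-of-mean calculation carried over from BCA-01 (the sponsor should confirm that it covered resistance), and that 26 were added for age overlap. Drop the suggestion that the total was derived for equation building.
2. State what 150 complete subjects give per equation: with an assumed 5 retained predictors, residual SD to about -10%/+13% and each 95% limit of agreement to about ±0.27 SD, both before allowing for selection.
3. Name as the accuracy figure the optimism-corrected error with its CI, from a bootstrap that repeats the whole stepwise selection for each equation. This requires the candidate list and the entry and removal rule to be written down first.

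Cost: no extra subjects, visits or measurements. The work is a resampling run for each equation and device (several outcomes, three devices, and two positions for the mBCA 525), fixing the candidate list, and an amendment that must await ethics committee approval under section 9.1. The reported accuracy will look slightly less favourable.

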1.4 Study Objective

The objective of the study is to develop prediction equations for calculating Fat-Free Mass (FFM), Total Body Water (TBW), Extracellular Water (ECW), Visceral Adipose Tissue (VAT), total Skeletal Muscle Mass (SMM) and segmental SMM in a sub-group of elderly persons. The prediction equations are based on linear regression analysis between the gold standard reference methods Air Displacement Plethysmography (ADP), Dual-energy X-ray Absorptiometry (DXA), Magnet Resonance Imaging (MRI), Deuterium dilution method (D_2O) and Sodium Bromide dilution method (NaBr) on the one hand and bioelectrical impedance measurements on the other hand.

Multi-frequency bioimpedance is measured for all body segments: right arm, left arm, right leg, left leg, trunk, right body side and left body side using the seca mBCA 515 and 555 in standing position and the seca mBCA 525 in lying position.

seca	Clinical Investigation Plan Inv. code: BCA-12 Doc. code: 25-02-02-456	Rev. date: 16-01-19 Revision: 1.4 Page: 14 of 32
-------------	---	--

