1.9 Subject Discontinuation Criteria

All subjects have the right to withdraw consent without prejudice at any time during the study. If a subject withdraws consent, the investigator should make a reasonable effort to determine the cause for withdrawal of consent. For these subjects, as well as for subjects who require permanent discontinuation from examination with the medical device, the investigator should make a reasonable effort to complete all required study procedures. All information should be documented in the subject's source data documents and on the Case Report Form (CRF). A subject who discontinues treatment will not be replaced. The subject's participation in this study should be permanently discontinued as a result of:

- formal withdrawal of informed consent
- investigator concludes that it is in the subject's best interest to discontinue study procedures
- presence of other medical conditions that prohibit continuation of study procedures
- subject is willingly or inadvertently non-compliant to any of the CIP procedures in the opinion of the investigator

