2. INVESTIGATIONAL DEVICES

The seca medical Body Composition Analyzer (mBCA) is mainly used in hospitals, medical practices and inpatient care facilities in accordance with national regulations.

The mBCA records weight, height and bioelectrical impedance measurements and automatically calculates parameters such as fat-free mass (FFM) which can be derived from them. The results are displayed in graphical form and assist the attending physician with the following medical issues:

- determining energy expenditure and energy reserves as a basis for nutritional advice
- assessing metabolic activity and the success of a training program, e.g. within the framework of rehabilitation or physiotherapy
- determining a patient's fluids status

The mBCA is not intended for use on children.

2.1 Model for standing bioimpedance measurement: mBCA 515

seca	Clinical Investigation Plan Inv. code: BCA-12 Doc. code: 25-02-02-456	Rev. date: 16-01-19 Revision: 1.4 Page: 16 of 32
-------------	---	--

Technical Data

General:

- Dimensions (W×H×D): 976 × 1,251 × 828 mm
- Display type: 8.4" touch-screen display, can be swiveled 180° to the left and right
- Power supply: Power adapter
- Voltage: 100 V – 240 V
- Interfaces: seca 360° wireless, USB 2.0, Ethernet
- Microsoft® Windows® compatible printer via seca 115 PC software

Bioelectrical Impedance Analysis:

- Measurement method: 8-point Bioelectrical Impedance Analysis
- Type of electrode: Stainless steel, three pairs of hand electrodes, two pairs of foot electrodes
- Measurement frequencies: 1; 1.5; 2; 3; 5; 7.5; 10; 15; 20; 30; 50; 75; 100; 150; 200; 300; 500; 750; 1,000 kHz
- Measurements: Impedance (Z), Resistance (R), Reactance (Xc), Phase angle (φ)
- Measurement range Impedance: 10 Ω to 1,000 Ω
- Measurement segments: Right arm, left arm, right leg, left leg, right half of body, left half of body, torso
- Measurement current: 100 µA
- Measurement time: max. 90 seconds for 19 frequencies

The seca mBCA 515 has an integrated calibrated scale with a maximum load of 300kg. More information about the technical data for the scale and technical modifications can be found at the instruction for use for doctors and assistants at chapter 13.

PC software seca analytics 115:

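### Every prediction equation is built by stepwise regression in the whole sample with no internal validation, so accuracy read from the fitting data will tend to look too good

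*Combined protocol and SAP*

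**What the plan says.** Section 3 (Study Statistics), repeated in the synopsis, is the whole statistical plan. Its only sentence on analysis is "The prediction equations shall be developed by stepwise multiple regression analysis". On size it says "The resulting sample size to generate a formula for elderly is N = 150". That number is the 124 carried over from study BCA-01 plus 26 subjects aged 60 to 65, added so that the age ranges overlap. The 124 was set by the confidence-interval width of a mean, with "the resistance measurement of the left body side (RI 50 kHz) being crucial for formula generation".

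Section 1.4 lists the targets: FFM, TBW, ECW, VAT, total SMM and segmental SMM. It ties the method to the reference measurements: "The prediction equations are based on linear regression analysis between the gold standard reference methods". On the predictor side it says "Multi-frequency bioimpedance is measured for all body segments: right arm, left arm, right leg, left leg, trunk, right body side and left body side". The mBCA 515 data in section 2.1 give "Measurement time: max. 90 seconds for 19 frequencies"; the mBCA 525 and 555 use 9 frequencies. Section 1.9 adds "A subject who discontinues treatment will not be replaced".

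The plan gives no candidate list, no entry or removal rule, no accuracy measure and no validation step.

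**The concern.** An equation chosen and fitted in one set of subjects matches those subjects better than it will match others from the same population. Accuracy measured in the fitting data carries that advantage. Stepwise selection can add to it, because terms that happen to fit well in this sample are the ones kept. As written, the plan produces no other kind of accuracy figure.

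The equations are the product of this study. Section 2 says of the device that it "automatically calculates parameters such as fat-free mass (FFM) which can be derived from them" and that the results assist the attending physician. Section 9.2 says the results are meant for publication. Users will judge the equations by their stated error.

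Two passages might seem to close the gap but do not. Section 2.4 speaks of cross-validating device results against the reference methods. Those methods supply the regression outcomes (section 1.4), so that comparison is not a test in independent data. The 26 extra subjects serve age overlap and are not a validation set.

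**Working it through.** **1. The plan's own figure.** 124 + 26 = 150, which reproduces. The 124 cannot be re-derived, because its SD, confidence level and interval width are not given. For a 95% interval for a mean it would correspond to a half-width of 1.96/√124 = 0.176 SD. That says nothing about the error of an equation.

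**2. Estimation error alone, no selection.** Take a pre-set list of p normally distributed predictors fitted in n subjects. The ratio of root mean squared new-subject error to residual SD (which SEE estimates), minus 1, is

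√[(n+1)(n−2) / (n(n−p−2))] − 1

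- n = 150, p = 6: √[151×148 / (150×142)] − 1 = √1.0492 − 1 = 2.4%
- n = 150, p = 10: √[22,348 / 20,700] − 1 = 3.9%
- n = 150, p = 15: √[22,348 / 19,950] − 1 = 5.8%
- n = 130 (assumed, since discontinued subjects are not replaced): 2.8%, 4.6% (rounded up from 4.55%) and 6.8% for the same p

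In 3,000 simulated data sets at n = 150, SEE lay below the true new-subject error in 67% (p = 6), 75% (p = 10) and 81% (p = 15). The bias is a tendency, not a certainty.

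**3. Stepwise with a short list.** All inputs are assumed: n = 150; 5 covariates with pairwise correlation 0.3; 1 or 10 impedance candidates; entry at p < 0.05 and removal at p > 0.10; impedance correlation 0.6 between segments and 0.5 between resistance and reactance; three impedance values carrying signal; residual SD 1.7; R-squared 0.965 (FFM-like) or 0.65 (VAT-like). There were 1,500 data sets per setting and 20,000 new subjects. Three frequency-correlation structures were used: adjacent correlation 0.98, adjacent correlation 0.90, and low-rank.

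| FFM-like, kg | SEE | New-subject error | Excess |
|---|---|---|---|
| 1 candidate, 0.98 | 2.107 | 2.166 | 2.8% |
| 1 candidate, 0.90 | 2.151 | 2.233 | 3.8% |
| 1 candidate, low-rank | 1.955 | 2.029 | 3.8% |
| 10 candidates, 0.98 | 1.686 | 1.771 | 5.0% |
| 10 candidates, 0.90 | 1.692 | 1.783 | 5.4% |
| 10 candidates, low-rank | 1.691 | 1.767 | 4.5% |

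The differences are 0.06–0.08 kg (1 candidate) and 0.08–0.09 kg (10 candidates). The VAT-like excess is 3.3–3.9% and 5.8–6.8%. Over both outcomes, limits of 1.96 × SEE cover 93.7–94.3% and 93.2–93.7% of new subjects. SEE fell below the true error in 68–75% and 75–87% of data sets.

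**4. Hypothetical large pool.** Seven segments × resistance and reactance × 9 frequencies = 126 values; with 19 frequencies, 266. Under the same structures (500 data sets each), the excess was 13.0–19.2% with 126 and 18.8–30.2% with 266. A separate simulation used equal pairwise correlation of 0.5, five true predictors and R-squared from 0.70 to 0.95. Its SEE was 3–4% too low with 10 candidates, 9–11% with 50 and 23–26% with 126. Restated as excess over SEE, the last is 1/(1−0.228) − 1 = 30% to 1/(1−0.256) − 1 = 34%. A third simulation gave 4.5% with 15 terms, 12% with 50 and 33% with 126. All agree on direction and on growth with the pool; the level depends on the assumed structure.

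**5. Does the remedy work?** With selection rerun inside 10-fold cross-validation, scenario averages were within −0.6% to +0.8% of true error for short lists and 0.0% to +2.8% for large pools. In the separate simulation (R-squared 0.85, 50 candidates, 40 data sets), root mean squared error was 1.506 in the fitting data, 1.732 cross-validated and 1.740 in new subjects. A simple bootstrap correction overshot at 1.880.

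**The case against.** The best case against has four parts.

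- **The harm is conditional.** The plan names no SEE, R-squared or limits of agreement, so it does not state a wrong analysis; it omits one. This stands, and the concern is worded accordingly.
- **The short-list effect is small and mostly not due to stepwise selection.** Section 3's stress on one resistance value hints at a short list, although it stands in the sample-size text and fixes nothing. With 10 candidates the FFM-like excess is 4.5–5.4%, against 5.8% for fitting all 15 terms without selection. With 1 candidate it is 2.8–3.8% against 2.4%. This also stands: for a short list, the missing validation matters more than the selection method.
- **The remedy is noisy.** In a single data set the cross-validated error has an SD of 5.8–6.8% with a short list, about as large as the bias. That is true, but SEE is itself about as variable. Without selection its SD was 5.8–6.1%, against 6.0–6.5% for cross-validation. The change removes a systematic bias for little added noise.
- **The large-pool figures are hypothetical, and the simulations differ on their size.** At 126 candidates they run from 13% to 34%. They show only how far the unstated candidate list could move the answer and should not be read as estimates for this study.

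It is also fair that section 2 describes the devices in general and does not say these equations will be loaded into them. None of this supplies the missing validation step.

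**Conclusion.** The concern holds. That the plan contains no internal validation, and that the sample size does not rest on equation accuracy, can be read directly from the documents. The direction of the bias is well established as an average tendency. Its size cannot be read from the documents, because the candidate list, the selection rule and the expected fit are not given. On assumed inputs with a short list, it is about 3–7% of SEE, or 0.06–0.09 kg for an FFM-like outcome, which is modest. It becomes substantial only if many impedance channels are offered, which the plan neither states nor rules out. This should be fixed because the equations are the study's main output and the correction costs very little. It does not undermine the design or the data collected.

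**What to change.** Add to section 3 and to the synopsis:

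> The final equation for each outcome is fitted in all evaluable subjects. SEE, bias and limits of agreement are reported from repeated 10-fold cross-validation, with all term selection rerun inside each training fold; values from the fitting data are shown only beside these.

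As a supporting step, state the candidate terms and the entry and removal rule for each outcome before analysis. This also settles how large the bias can be. Other resampling schemes are acceptable if they repeat the selection, but the simple bootstrap correction overshot with 50 candidates.

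The cost is a few sentences of plan text and some computing. No subject is given up for validation, no new subjects or measurements are needed, and the method can be applied to the data as collected. Reported accuracy will on average be slightly less favourable, and in a single study of this size it will still carry sampling variation of about 6% (SD) with a short list.
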